Clinical Trial Protocol
Biochemical and Reno-Protective Effects of Remote Ischemic Preconditioning on
Contrast-Induced Kidney Disease (BRICK) Trial

Version	Date	Main reason for changes
1	12/20/2017	Not applicable
2	02/26/2019	Addition of a second trial site

1. *Background*

Acute kidney injury (AKI) is a common complication of intravenous, iodinated contrast media, that is widely used for cardiac catheterization and percutaneous coronary intervention (PCI) in patients with coronary artery disease (CAD).^{1,2} In the United States, CAD remains the number one cause of death in both men and women despite improvement in the care of patients over the last decade. Although PCI restores blood flow to the heart, the contrast media used for the procedure can cause AKI, possibly mediated by contrast-induced vasoconstriction of renal blood vessels and free radical-mediated direct renal tubular toxicity. The incidence of AKI is estimated to range between 10 and 40% in patients undergoing cardiac catheterization with higher rates in patients with acute myocardial infarction.^{1,2} In the United States, approximately 1.4 million cardiac catheterization procedures are performed each year, and this estimate is expected to increase exponentially in the next few decades. With increasing use of contrast media, the prevalence of AKI is also expected to rise. AKI predicts elevated risk of heart attack, longer in-hospital stay, more complicated hospitalization course, and higher in-hospital mortality. Unfortunately, there is no effective prophylactic regimen to prevent AKI.

Remote ischemic pre-conditioning (RIPC), elicited by application of one or more brief episodes of ischemia and reperfusion of a limb, is a promising therapy for preventing or attenuating AKI. Given that renal ischemic injury and tubular toxicity are the most common pathophysiological concepts of AKI, it stands to reason that RIPC may prevent AKI via nitrite-induced vasodilation and damage associated molecular protein -mediated renal cell protection. Our preliminary data suggest that RIPC provides renal protection and indicate a connection between RIPC-induced changes in protective molecules (nitrite, cyclic guanosine

monophosphate [cGMP]), tissue inhibitor of metalloproteinases 2 [TIMP-2], and insulin-like growth factor-binding protein 7 [IGFBP7] and organ protection. However, the effect of RIPC on AKI in patients with CAD undergoing cardiac catheterization is not well-established, and the underlying mechanism of such effect remains unclear.

2. Study Design and Objective

This is a prospective, double-blinded, two-center, randomized, sham-controlled clinical trial. The primary aim of this study is to determine whether remote ischemic preconditioning (RIPC) reduces the incidence of acute kidney injury (AKI) in high-risk patients undergoing coronary angiography and/or PCI. The secondary aim is to study the effect of RIPC on renal (TIMP-2 X IGFBP7) and vascular (cGMP) biomarkers, major adverse cardiac events (MACE), and major adverse kidney events (MAKE) during a 6-month follow-up period in high-risk patients undergoing coronary angiography.

3. Patient

Eligible male and female patients over the age of 18 years with unstable angina or non-ST elevation myocardial infarction (NSTEMI) who are at high risk for AKI and undergoing coronary angiography and/or PCI. The trial will be conducted at two tertiary hospitals in the United States, the University of Pittsburgh Medical Center and the affiliated Veterans Affairs Pittsburgh Healthcare System. AKI risk will be determined by a modified version of Mehran's risk score. The scoring system contains different risk factors, including patient characteristics, comorbidities and contrast volume. At the time of enrollment and prior to coronary angiography, the lowest range of contrast volume (1-100) in the scoring system will be utilized for calculation of modified Mehran risk score as shown in Table 1.³ After coronary angiogram, the actual volume of contrast used during the procedure will be utilized to calculate post-angiography Mehran risk score. A score of 11 or higher will be used to define patients at high risk for AKI as shown in Table 2.³ Patients with inability to provide informed consent, acute ST elevation myocardial infarction, unstable blood pressure (BP) (systolic BP > 200 or <90 mmHg), peripheral vascular disease, contrast allergy, renal disease requiring dialysis, or placement of arteriovenous fistula graft will be excluded.

Table 1: Scoring System for Predicting Acute Kidney Injury

Risk Factors	Score
Age > 75	4
Diabetes mellitus	3
NYHA Class III/IV Heart failure	5
Anemia (male: HCT<39, female: HCT<36)	3
Hypotension (SBP<80mmHg or >1hr inotropic support)	5
Intra-aortic balloon pump placement	5
Estimated GFR < 20ml/min	6
Estimated GFR 20-40 ml/min	4
Estimated GFR 40-60ml/min	2
Contrast volume (1-100cc)	1
Contrast volume (101-200cc)	2
Contrast volume (201-300cc)	3
Contrast volume (301-400cc)	4
Contrast volume (401-500cc)	5

Table 2: Risk Score and Predicted Risk of Acute Kidney Injury and Dialysis

Mehran Risk Score	Risk of AKI	Risk of Dialysis
≤ 5	7.5%	0.04%
6-10	14%	0.12%
11-16	26.1%	1.09%
>16	57.3%	12.6%

Inclusion Criteria

- Adult patients over the age of 18 years
- Diagnosis of non-ST elevation myocardial infarction or unstable angina
- Referral for invasive coronary angiogram and/or percutaneous coronary intervention
- Acute kidney injury risk score of ≥ 11

Exclusion Criteria

- Inability to give informed consent
- Unstable blood pressure (systolic blood pressure > 200 or < 90 mmHg)
- History of allergy to contrast media
- Peripheral vascular disease of upper limb
- Renal disease requiring dialysis
- Placement of arteriovenous fistula and arteriovenous graft

4. Randomization and Blinding

A total of 110 patients will be randomized to the RIPC (55) treatment group or the Sham-RIPC (55) control group on a 1:1 basis. Randomization will be computer-generated using the REDCap data management application system. Unblinded statistician will set up a pre-defined allocation table with variable block sizes of 2 to 4, and stratification by site. Unblinded research staff will perform randomization and application of RIPC and sham-RIPC. Patients will be blinded by the use of Sham-RIPC in the control group. Investigators, cardiologist performing coronary angiography, clinical outcome assessors, and data analysts will be unaware of treatment assignment.

5. Procedures, blood and urine sampling and analysis

All patients will undergo coronary angiography and/or PCI using the standard technique. The decision to perform PCI, choice of guidewires, balloons, stent types, and characteristics will be made by the interventional cardiologist according to common laboratory practice and guideline for coronary angiography and interventions. All patients will receive standard medical therapy and hydration for coronary angiography and PCI. We will extract data on patient demographic and medical history including gender, age, race, comorbidities, and coronary angiography

findings from the electronic medical record.

After randomization, we will perform RIPC or Sham-RIPC approximately 1-4hrs before coronary angiography. The patients assigned to RIPC will undergo 3 cycles of 5-minute inflation of a standard blood-pressure cuff to 200 mmHg, followed by 5-minute cuff deflation. In patients assigned to the control group, sham-RIPC will be induced using 3 cycles of 5-minute blood pressure cuff inflation to a pressure of 10 mmHg, followed by 5-minute cuff deflation.

For the primary aim outcome of AKI, blood samples will be drawn at baseline and then at 24hrs and 48hrs after coronary angiography for measurement of serum creatinine using the standard laboratory protocol. Urinary insulin-like growth factor-binding protein 7 (IGFBP7) and tissue inhibitor of metalloproteinases 2 (TIMP-2), both inducers of G1 cell cycle arrest, are implicated in AKI and serve as biomarkers to predict it.⁴ The product of urinary TIMP-2 and IGFBP7 concentrations, (TIMP-2) \times (IGFBP7), will be measured with the NephroCheck Test. We will measure urinary TIMP-2 \times IGFBP7 from samples obtained at baseline, immediately after three cycles of RIPC but before coronary angiography, 24hrs, and 48hrs after coronary angiography. These assays will be performed at the Center for Critical Care Nephrology core laboratory at the University of Pittsburgh according to the standard manufacturer's specification. Plasma concentration of cyclic guanylate monophosphate (cGMP) will be measured using blood samples obtained at baseline, immediately after 3 cycles of RIPC but before coronary angiography, 24hrs, and 48hrs after coronary angiography. These assays will be performed at the Center for Microvascular Research laboratory at the University of Pittsburgh using the standard enzyme immunoassay kit.

6. Outcomes

The primary end point is the occurrence of AKI, defined as a relative increase in serum creatinine of $\geq 0.3\text{mg/dl}$ compared with baseline creatinine within 48 hours after coronary angiography according to the Kidney Disease: Improving Global Outcomes guideline.⁵ Secondary biomarker endpoints include the product of urinary concentrations of TIMP-2 and IGFBP7 and plasma concentration of cGMP. Other secondary clinical outcomes are 1) major adverse cardiovascular and

cerebrovascular events (MACCE) including rehospitalization for myocardial infarction, repeat revascularization, hospitalization for heart failure, stroke, and cardiac death and 2) major adverse kidney events (MAKE) including use of renal replacement therapy and all-cause death during the 6-month follow up.

7. *Statistical analysis*

Sample size and power analysis for the primary outcome: Limited data are available for estimation of sample size for the effect of RIPC on incidence of AKI in high-risk patients with unstable angina or NSTEMI undergoing coronary angiography or PCI. Assuming an estimated incidence rate of AKI of 36-40% in high-risk study population as documented in prior studies, and considering absolute risk reduction (ARR) of 26-28% as reported in trials performed in patients at moderate to high risk for AKI,^{6,7} a sample size of 100 patients (50 RIPC and 50 Sham-RIPC) will provide 88% power to detect a 25% ARR in the RIPC group (i.e. incidence of AKI is 35% in controls and 10% in RIPC group). Relative powers for different levels of effect sizes for our estimated sample size (N=100) are shown in the Table 1 below. We will enroll 110 patients to allow for up to 10% loss to follow up.

Table 1: Estimated Power with N=100 at Various Effect Sizes

		AKI Incidence (RIPC Arm)		
		10%	15%	20%
AKI Incidence (Sham-RIPC)	30%	73%	44%	21%
	35%	88%	65%	39%
	40%	95%	81%	59%

Descriptive Statistics: Baseline socio-demographic and clinical characteristics will be summarized using mean and standard deviation when normally distributed, and median and interquartile range when not normally distributed. Categorical variables will be summarized using relative frequencies and percentages.

Primary outcome: the goal is to determine whether RIPC reduces the rate of AKI in high-risk patients undergoing coronary angiography and/or PCI. As this is a categorical variable with an expected reduction in AKI rate, the hypothesis will be tested using risk ratio to determine if the difference in incidence of AKI is significantly lower in RIPC group compared to the Sham-RIPC group. We will explore baseline variables for univariable associations with AKI and examine for independent association of RIPC with AKI using logistic regression. The primary

analyses will be based on intention-to-treat principle.

Secondary outcomes (biomarkers): the goal is to characterize changes in the product of TIMP2 and IGFBP7 and plasma cGMP following RIPC in patients with CAD undergoing coronary angiogram. We will test the association of RIPC with levels of each molecule (RIPC vs. non-RIPC groups) using parametric statistics (t-test, confidence intervals for differences) when levels were normally distributed (expected), or using transformed levels if not. If distributions are very unbalanced, nonparametric tests will be used. The extent of protocol violations and missing outcome data will be quantified overall and by random assignment. All statistical analyses will be performed using SPSS.

8. *Ethics*

The written informed consent form, and overall study protocol and materials will be reviewed and approved by the IRB before the initiation of this trial. A Data and Safety Monitoring Board (DSMB) will be created to review this study. The DSMB will meet after initial approval with plan for quarterly meeting. However, the follow-up meeting frequency of the DSMB will be determined during the first meeting. An emergency meeting of the DSMB will be called at any time by the Chairperson should questions of patient safety arise.

9. *Informed consent*

All study patients will be provided with an easily understandable informed consent form approved by the IRB. The patients will be enrolled after signing the informed consent form. The informed consent form will be kept as an important document of the clinical trials for future reference.

References

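### Do the two wordings of the peripheral vascular disease exclusion in Section 3 call for a change to the plan?

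*Combined protocol and SAP*

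**What the plan says.** Section 3 (Patient) gives the exclusions first as a sentence and then as a headed list. The sentence covers "peripheral vascular disease, contrast allergy, renal disease requiring dialysis, or placement of arteriovenous fistula graft will be excluded", with no anatomical site for the vascular disease. The list under Exclusion Criteria has "Peripheral vascular disease of upper limb". The protocol mentions peripheral vascular disease nowhere else, does not define it, and does not give either statement precedence. The version table explains version 2 by the added site and says nothing about eligibility wording.

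The procedure text does not settle the matter. Section 5 describes "3 cycles of 5-minute inflation of a standard blood-pressure cuff to 200 mmHg" for the active arm, and for the control arm "sham-RIPC will be induced using 3 cycles of 5-minute blood pressure cuff inflation to a pressure of 10 mmHg". Neither sentence names the limb. The Background describes the technique only in general terms, as "elicited by application of one or more brief episodes of ischemia and reperfusion of a limb".

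**The concern.** Two statements of one exclusion that classify the same patient differently are a natural thing for a reviewer to flag. A patient with disease confined to the legs could be turned away by one screener and enrolled by another, each following the protocol. Section 3 also says "The trial will be conducted at two tertiary hospitals in the United States", so more than one team reads the text.

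Three things might be at stake. The first is the population to which the result applies. The second is the count of eligibility deviations, since Section 7 commits to quantifying protocol violations overall and by assignment. The third is whether the exclusion covers the limb that is cuffed, given that Section 5 does not name it.

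**Working it through.** The plan has no figure of its own on this point, so the check is a comparison of the texts, followed by a look at what depends on them.

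**1. How each wording classifies a patient**

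| Site of vascular disease | Section 3, sentence | Section 3, list |
|---|---|---|
| None | not excluded | not excluded |
| Upper limb, alone or with other sites | excluded | excluded |
| Only outside the upper limb | excluded | not excluded |

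The two statements part company in the last row only.

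**2. How many patients fall in that row**

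If a proportion p of otherwise eligible patients have disease only outside the upper limb, then under the list wording about 110 × p of those enrolled would be such patients, and under the sentence wording none would. The documents give no value for p and none is assumed here. The steps below hold for any p, including zero.

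**3. Effect on the comparison between arms**

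The criterion is a baseline characteristic, applied before assignment and in the same way to both arms. Section 4 randomizes 1:1 from a pre-defined allocation table, stratified by site. Even if the two hospitals read the criterion differently, assignment would still be balanced within each hospital. Section 7 bases the primary analysis on intention to treat, so a randomized patient is analysed as assigned whichever wording was used at screening.

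**4. Effect on sample size and power**

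The enrolment target is fixed at 55 + 55 = 110 under either wording. The stated 88% power rests on 50 patients per arm and AKI incidences of 35% and 10%. None of these inputs refers to vascular disease. The risk score that defines high risk (Section 3, Table 1) has no vascular disease item, so the entry threshold of 11 works identically under both wordings.

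**5. The cuffed limb**

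Under the sentence, vascular disease of any limb is excluded, so the cuffed limb is covered whichever it is. Under the list, upper-limb disease is excluded, and the cuffed limb is covered if the cuff goes on an arm. The exclusion would miss the cuffed limb only if the list governs and a leg is cuffed. No text suggests the latter; the list wording and the standard blood-pressure cuff both point to the arm. That Section 5 leaves the limb unnamed is a separate missing detail, not part of this inconsistency.

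**The case for a change.** The strongest case for acting is that the contradiction is literal, both statements are current text, and the repair is cheap. It can be added that the list is not simply the fuller version of the sentence. The sentence also names acute ST elevation infarction ("Patients with inability to provide informed consent, acute ST elevation myocardial infarction"), which the list omits, so a reader cannot take it for granted that the list supersedes. With two hospitals recruiting, an eligibility deviation on this criterion could not be identified without doubt.

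Part of this stands. The wordings do differ, no precedence rule exists, and a report should make clear which one was applied.

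The rest carries less weight. The missing infarction item costs the list little, because the inclusion criterion "Diagnosis of non-ST elevation myocardial infarction or unstable angina" already covers it for the most part, and it says nothing about vascular disease. The fistula and graft item points the other way: the list spells out what the sentence runs together, as one expects of a formal list that follows a prose summary. That there are two hospitals does not show that they would read the criterion differently, since both work from one protocol.

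**Conclusion.** The inconsistency is genuine but small, and no change to the design or analysis follows. It affects one class of patient, those with vascular disease only outside the upper limb. Their number is unknown and may be zero. Following either wording gives a valid randomized comparison with the same target of 110, the same endpoint, the same analysis and the same stated 88% power. Aligning the text would remove no bias and improve no estimate.

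This rests on two assumptions. One is that eligibility is decided before, and without knowledge of, the next assignment. Section 4's allocation procedure implies this, although the protocol does not say who screens. The other is that trial staff work from the headed list or otherwise settle on one reading, as a study team ordinarily would.

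The two statements in Section 3 should still be reconciled as a matter of housekeeping, with the choice left to the clinical team, and the trial report should describe the exclusion as it was applied. That is an editorial clarification and not a revision of the statistical plan.

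### Does intention-to-treat on 110 patients, with power on 100, need a written rule for patients without an AKI outcome?

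*Combined protocol and SAP*

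**What the plan says.** Section 4 (Randomization and Blinding) randomizes 110 patients, 55 per arm. Section 7 (Statistical analysis) computes power on fewer: "a sample size of 100 patients (50 RIPC and 50 Sham-RIPC) will provide 88% power", for AKI rates of 35% and 10%. The difference is the allowance for loss: "We will enroll 110 patients to allow for up to 10% loss to follow up". The same section states that the primary "analyses will be based on intention-to-treat principle".

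Section 6 (Outcomes) defines AKI as a creatinine rise of at least 0.3 mg/dl "compared with baseline creatinine within 48 hours after coronary angiography". Section 5 schedules creatinine at baseline, 24 hours and 48 hours.

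The only text on absent outcomes is at the end of Section 7: "The extent of protocol violations and missing outcome data will be quantified overall and by random assignment". No section names an analysis set, gives a rule for a missing AKI outcome, or deals with a patient who has only one of the two later samples.

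**The concern.** Read strictly, intention-to-treat covers all 110, while the power figure covers 100. The ten or so patients in between might be dropped (denominator about 100) or kept and counted as having no AKI (denominator 110). The second rule treats a lost patient as a protected one. If more RIPC patients than sham patients lack a result, it manufactures benefit, and a blinded analyst who applied it would make the same error.

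There is also a conceivable route to unequal loss. In one arm patients "will undergo 3 cycles of 5-minute inflation of a standard blood-pressure cuff to 200 mmHg"; in the other there is "blood pressure cuff inflation to a pressure of 10 mmHg". Further, "Unblinded research staff will perform randomization and application of RIPC and sham-RIPC". In a trial of this size, a few patients moved in or out of the denominator can carry a result across 0.05.

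**Working it through.** **Inputs.** From the protocol: 55 randomized per arm (Section 4); 50 per arm for power, 35% v 10% AKI, up to 10% loss (Section 7). Assumptions, because the documents do not give them: two-sided alpha 0.05, Pearson chi-square without continuity correction, any split of losses by arm, and the same AKI rate in lost and retained patients of an arm. Section 7 names the risk ratio as the test measure; chi-square is used because it reproduces the plan's power table.

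**1. The plan's own figure.** The unpooled standard error is √(0.35×0.65/50 + 0.10×0.90/50) = √0.00635 = 0.0797. Then 0.25/0.0797 − 1.96 = 1.18, and Φ(1.18) = 0.88. Exact enumeration of the chi-square test gives 87.7%. The stated 88% reproduces. Enrolment is 100 × 1.10 = 110, so the plan allows for 10 lost.

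**2. Equal loss, 5 per arm, 35% v 10%.**

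| Rule | Sham | RIPC | Risk ratio | Exact power |
|---|---|---|---|---|
| Left out | 17.5/50 = 35.0% | 5/50 = 10.0% | 0.286 | 87.7% |
| Scored no AKI | 17.5/55 = 31.8% | 5/55 = 9.1% | 0.286 | 87.2% |
| Scored AKI | 22.5/55 = 40.9% | 10/55 = 18.2% | 0.444 | 79.0% |

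The first two rules reach different verdicts in 0.5% of trials. The third is an extreme and differs even with equal loss.

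**3. Ten lost at random.** The number lost from RIPC is hypergeometric (110 patients, 55 in RIPC, 10 drawn). An exact 5/5 split has probability 0.258. Averaged over the splits, leaving out and scoring no AKI give different verdicts in 2.7% of trials at 35% v 10%, 5.2% at 35% v 15% and 5.7% at 35% v 20%. With 35% in both arms, the chance of a false finding of benefit is 2.6% under both rules (nominal 2.5%), so there is no average bias.

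**4. More loss in RIPC, no true effect (35% in both arms).** Let x ~ Bin(55 − sham lost, 0.35) and y ~ Bin(55 − RIPC lost, 0.35). Compare x/(55 − sham lost) with y/(55 − RIPC lost), or x/55 with y/55.

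| RIPC/sham lost | False benefit, left out | False benefit, scored no AKI |
|---|---|---|
| 4/1 | 2.6% | 4.0% |
| 7/3 | 2.6% | 4.5% |
| 8/2 | 2.6% | 6.0% |
| 10/0 | 2.5% | 10.4% |

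In the other direction (7 sham, 3 RIPC lost, 35% v 10%), power is 87.7% left out and 82.2% scored no AKI. By chance alone, 8 or more of ten losses fall in RIPC with probability 4.7%, and all ten with probability 0.06%.

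**5. A single trial near the boundary, 7 RIPC and 3 sham lost.** Leaving out gives 16/52 v 7/48, p = 0.055. Scoring no AKI gives 16/55 v 7/55, p = 0.035. A Wald test on the log risk ratio also crosses 0.05 (0.066 v 0.044); Fisher's exact test does not (0.062 v 0.059).

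**6. Which rule the text implies.** Power rests on the patients left after loss, so the lost ones contribute neither an event nor a denominator. Section 7 then describes them as having missing outcome data, to be counted by arm. Neither statement fits with recording them as event-free.

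**The case for a change.** The strongest case for a change is that intention-to-treat fixes the arm in which a patient is analysed, not the value of an outcome nobody measured. Both denominators can therefore be called intention-to-treat, and step 5 shows the same patients giving opposite verdicts. Imbalance needs no special cause: a split of 7/3 or worse, in one direction or the other, arises by chance in 32% of trials with ten lost. A sentence or two before unblinding would cost almost nothing.

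Part of this stands. The plan is silent, and its silence on patients with only a 24-hour sample is the harder gap, because leaving out patients without any result does not settle it. The documents do not say how many such patients to expect.

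The rest is weaker. The inflated error comes only from the rule that the sample-size text points away from. The cuff procedure ends before angiography, while the outcome is a laboratory value 24 to 48 hours after it. Section 4 blinds patients, investigators and outcome assessors, so the route from cuff pressure to a missed creatinine sample is speculative. Reporting missing data by arm is good practice, not a sign that imbalance is expected.

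A more elaborate written rule is not automatically safer. Suppose a patient with only a 24-hour sample is counted when it shows AKI and dropped when it does not. Inclusion then depends on the result. With no true effect, 50% to 70% of AKI assumed visible at 24 hours, and ten 48-hour samples missing, false benefit is 3.5% to 3.9% for a split of 8 sham/2 RIPC and 4.4% to 5.4% for 10/0. If every patient without a 48-hour sample is left out, the figures are 2.2% and 2.9%. Acceptance windows, or scoring rules for early dialysis or death, would likewise add content for which the documents offer no basis.

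**Conclusion.** No change is called for. This is missing detail that a competent analyst fills in the way the plan's own arithmetic implies: analyse patients in the assigned arm, leave those without an AKI result out of the denominator, and report how many are missing in each arm. The 110 and the 100 do not conflict; one is the other inflated for loss.

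On that reading the 88% stands, and the false-benefit rate stays at 2.5% to 2.6% in the RIPC-heavy splits of step 4. The alternative costs about half a point of power with equal loss and has no average bias with random loss. It does harm only when lopsided loss combines with a scoring rule that the documents do not suggest. The by-arm count of missing outcomes in Section 7 would show a reader whether such loss had occurred.

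This rests on two-sided alpha 0.05, a chi-square test and loss unrelated to AKI within each arm. If loss depends on outcome, leaving patients out can also mislead, and the documents give no figure from which to size that.

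### The primary AKI test uses neither the randomization stratum (site) nor the enrolment Mehran score; stratifying by both is a low-cost improvement, not the repair of an error

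*Combined protocol and SAP*

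**What the plan says.** - **Primary test (Section 7, Primary outcome).** The plan says that "the hypothesis will be tested using risk ratio to determine if the difference in incidence of AKI is significantly lower in RIPC group". It names no stratum, covariate, test statistic, alpha or sidedness.
- **Adjusted analysis (same paragraph).** "We will explore baseline variables for univariable associations with AKI and examine for independent association of RIPC with AKI using logistic regression". The covariates are not named, and the model is not labelled supportive.
- **Randomization (Section 4).** The plan calls for a "pre-defined allocation table with variable block sizes of 2 to 4, and stratification by site".
- **Enrolment score (Section 3).** Before angiography, "the lowest range of contrast volume (1-100) in the scoring system will be utilized for calculation of modified Mehran risk score". Eligibility requires "Acute kidney injury risk score of ≥ 11", so two bands of Table 2 are enrolled: 11-16 (predicted AKI risk 26.1%) and >16 (57.3%).
- **Second score (Section 3).** After the procedure, "the actual volume of contrast used during the procedure will be utilized to calculate post-angiography Mehran risk score".
- **Planning rate (Section 7, Sample size).** "Assuming an estimated incidence rate of AKI of 36-40% in high-risk study population as documented in prior studies"; the headline power calculation uses 35% against 10%.

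**The concern.** The natural reading of Section 7 is that a crude risk ratio carries the hypothesis test and the logistic regression comes second. On that reading, the factor used to stratify randomization drops out of the primary analysis. So does the baseline measure that the protocol itself treats as the main predictor of AKI.

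The Mehran score is not a randomization stratum either, so nothing in the design balances it. With about 50 patients per arm, one arm can by chance receive noticeably more patients scoring above 16. A crude comparison then mixes that difference with the treatment effect. The logistic model does not settle the matter, because its covariates are chosen after looking at associations with the outcome and the plan does not say which result governs. An imbalance seen after unblinding would invite an argument about adjustment that one prespecified sentence could prevent.

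**Working it through.** **1. The plan's own figure.** For 35% against 10% with 50 per arm, the unpooled normal formula gives z = 0.25 / √(0.35×0.65/50 + 0.10×0.90/50) = 0.25 / 0.0797 = 3.14. Power is then Φ(3.14 − 1.96) ≈ 88%, as stated. Exact enumeration of an uncorrected two-sided 5% chi-square test reproduces the whole power table within 1 point:

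| Sham-RIPC rate | RIPC 10%: stated / exact | RIPC 15% | RIPC 20% |
|---|---|---|---|
| 30% | 73 / 73.4 | 44 / 44.3 | 21 / 21.2 |
| 35% | 88 / 87.7 | 65 / 65.2 | 39 / 39.3 |
| 40% | 95 / 95.4 | 81 / 81.9 | 59 / 59.5 |

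The plan was therefore sized for an unadjusted two-sided 5% test. A one-sided 5% test would give 92.1% for 35% against 10%.

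**2. What Table 2 implies.** The gap between bands is 57.3 − 26.1 = 31.2 points. If it applies to enrolment scores, a 10-point imbalance in the >16 share shifts the crude control-risk difference by 0.10 × 31.2 = 3.1 points. The share needed for a given control rate is (rate − 26.1)/31.2: 28.5% for a rate of 35%, 31.7% for 36% and 44.6% for 40%. Shares of 10% and 20% give control rates of 29.2% and 32.3%.

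**3. Low shares are plausible.** With contrast fixed at 1 point, age >75 (4), diabetes (3), NYHA III/IV (5) and anemia (3) bring the total to 16. Leaving out hypotension and balloon-pump points, a score above 16 therefore needs all four with eGFR <60, or three of them with eGFR <40 (for some combinations <20).

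**4. Simulation.** There were 40,000 trials per scenario with 100 patients and permuted blocks of 2 and 4 within site. Assumptions that the documents do not supply: Table 2 risks hold for enrolment bands; the >16 share is 10, 20, 28.5 or 44.6%; sites split 70/30; sites differ by 0 or 20 points; the risk ratio is constant.

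The crude uncorrected chi-square was compared with the uncorrected Mantel-Haenszel statistic, [Σ(a_k − n_1k m_k/n_k)]² / Σ[n_1k n_0k m_k (n_k − m_k) / (n_k²(n_k − 1))]. Here, in stratum k, a_k is RIPC events, m_k all events, n_1k and n_0k the arm sizes, and n_k the total. The pooling rule was: band alone if any site-by-band cell has fewer than 10 patients; site alone if the >16 band has fewer than 10.

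Type I error over all trials was 4.6-5.3% crude and 4.7-5.1% stratified. Power at risk ratio 15/35 with no site difference was:

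| Share >16 | Trials with imbalance ≥10 points | Crude power in those: RIPC has fewer / more high-band patients | Stratified power: fewer / more | Average over all trials: crude / stratified |
|---|---|---|---|---|
| 10% | 12% | 68 / 43% | 56 / 51% | 55.3 / 55.0% |
| 20% | 25% | 74 / 46% | 60 / 59% | 60.6 / 61.2% |
| 28.5% | 31% | 78 / 52% | 66 / 66% | 65.3 / 66.6% |
| 44.6% | 36% | 84 / 61% | 74 / 74% | 73.1 / 74.7% |

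As a check on the second column, the standard deviation of the between-arm difference in share at 28.5% is √(2×0.285×0.715/50) = 9.0 points, so gaps of 10 points are not rare. In the imbalanced trials crude type I error is 6.1-6.8%, offset by 4.0-4.8% in the rest. A separate simulation under the same assumptions agreed within simulation noise, except that the 10% share gave a slightly wider stratified swing (59 / 51%).

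**5. Average power.** For risk ratios from 10/35 to 20/35, stratified minus crude is -0.7 to +0.3 points (10% share), +0.3 to +1.0 (20%), +0.6 to +1.5 (28.5%) and +0.7 to +3.0 (44.6%). Without pooling, the 10% share gives about -2 to 0.

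**6. If Table 2 overstates the gap** (28.5% share, 35% against 15%). With half the gap (15.6 points), the crude swing shrinks to 71 / 59%, and average power is 64.1% stratified against 64.8% crude. With no gap it is 63.9% against 64.8%, a cost of 0.9 points and the worst found with pooling.

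**7. The logistic model.** With assumed screens of p<0.05 to p<0.20 and 4 to 12 null covariates, the screened model alone has type I error of 4.4-5.3%. It reaches 5.6-7.2% only if either the crude or the logistic result may be claimed.

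**The case against.** The strongest reply is that nothing is broken. The crude test is valid and conventional, and the average gain is near zero. The 78 / 52% contrast applies only to imbalanced trials, and only if Table 2 transfers to a score that fixes contrast volume at its lowest range. The benefit is largest at shares that the scoring table gives least reason to expect. All of this is true, and it is why the point is an improvement and not an error.

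The case for site is weak on average power. With a common odds ratio, a 28.5% share and 35% against 10%, stratifying by site alone gives 87.5%, against 87.7% crude, 89.1% by band and 88.7% by both. Site matters only if the sites differ strongly: with a site odds ratio of 4 and a 50:50 split, crude type I error falls to 4.1%, and stratifying by both adds 2.0 to 4.3 points of power. The pooling rule leaves the site-by-band strata in 100, 94, 66 and 8% of trials at the four shares. The second site was added only in version 2, so it may be small; at 90/10, with shares of 10, 28.5 or 44.6%, the full stratification was never used. Band alone would be within about 1 point of four strata. That argues for a sensible pooling rule. It does not argue for leaving both factors out.

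The logistic regression would show an imbalance, and its type I error is acceptable on its own. It still does not govern the conclusion, and its covariates are open. The missing alpha, sidedness and test statistic are a separate gap and add no weight here.

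**Conclusion.** The concern holds at the level of a recommended change. The primary test ignores the randomization stratum and a strong baseline predictor that is already recorded, while remaining a valid test.

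The gain from stratifying is stability, not average power. At shares of 20% or more, a quarter to a third or so of trials have an imbalance of 10 points or more. In these, the stratified result hardly depends on which arm drew more high-risk patients, whereas crude power differs by 23 to 28 points. At a 10% share the swing narrows without disappearing. The average power change runs from -0.9 to +3.0 points.

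Confidence is medium, because the share scoring above 16, the site split, any site difference and the transfer of Table 2 to enrolment scores are all assumptions.

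**What to change.** Write the following into the SAP before unblinding.

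- **One primary analysis.** A two-sided 5% Cochran-Mantel-Haenszel test without continuity correction, stratified by enrolment Mehran band (11-16, >16) and site. Write the statistic out so that it does not depend on a software default, and state that it governs the conclusion.
- **A pooling rule applied to blinded counts.** For example: if any site-by-band cell has fewer than 10 patients, both arms together, stratify by band alone; if the >16 band has fewer than 10, stratify by site alone. Also say what happens if a site is itself that small, which this example leaves open.
- **Effect estimate.** The Mantel-Haenszel risk ratio with 95% CI. In 1.4-4.3% of simulated trials with an effect, this interval and the test disagree, so the governing result must be named.
- **Not the post-angiography score.** It includes contrast volume recorded after randomization.
- **Logistic regression.** Label it supportive, with site and enrolment score as fixed covariates and no univariable screening for the treatment effect.

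The cost is wording only. Both factors are already recorded, N and the power table stand, and the primary test has to be written out in any case. The downside is up to about 1 point of average power with pooling, or about 2 without it, if few patients score above 16 or the band gap is smaller than in Table 2.
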